5.12.1 Adverse Events

Adverse events will be coded by system organ class and preferred term using the MedDRA dictionary, version 18.1.

An AE will be considered a treatment-emergent adverse event (TEAE) if it started after the first dose of study drug or started prior to the first dose of study drug but increased in severity after the first dose of study drug.

The incidence of TEAEs will be presented by system organ class and preferred term. The incidence of Severe TEAEs, TEAEs related to study drug, TEAEs leading to discontinuation of study drug, and treatment-emergent serious adverse events (SAEs) will also be presented, separately, by system organ class and preferred term. If a patient has more than 1 AE coded to the same preferred term, the patient will be counted only once for that preferred term using the highest severity and closest relationship to study drug.

The incidence of common (\geq 3% of patients in any treatment group) TEAEs will be presented using preferred terms by decreasing frequency in the IW-3718 overall group.

Data listings will be provided for deaths, SAEs, and AEs leading to discontinuation of study drug.

Additional analyses will be conducted on constipation as an AE of interest. Median time from study drug initiation to onset of the first occurrence of constipation will be estimated using the Kaplan-Meier method. Duration of treatment-emergent constipation will also be summarized. If a patient had multiple occurrences of treatment-emergent constipation, the occurrence with the longest duration will be used in the summary.

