IW-3718 has been evaluated in a Phase 2a study. This study was a 4-week, randomized, double-blind, placebo-controlled, proof-of-concept study in patients with GERD not completely responsive to QD PPI therapy. In this study patients were randomized in a 1:1 fashion to either IW-3718 1000 mg bid or placebo. A Bilitec procedure was performed as an optional procedure. Esophageal duodenogastroduodenoscopy and pH monitoring were not required, but results were collected if these procedures were performed prior to randomization or in the recent past. Symptoms were assessed over the four week period to determine severity of heartburn-related symptoms.

Safety and efficacy data are available for 93 patients, 46 of whom received 1000 mg IW-3718 BID. IW-3718 was well tolerated among patients with GERD. There were no deaths or study medication-related serious adverse events (SAEs). Common TEAEs (>5% of patients) among patients who received IW 3718 or placebo included constipation (13% vs 0%) and abdominal pain (7% vs 2%).

In this study, among all patients (Intent-to-treat [ITT] Population), severity of daytime heartburn showed a trend toward being numerically reduced in IW-3718 patients compared to placebo ($p=0.124$). The largest differences between IW-3718 and placebo for this parameter were seen in patients who underwent Bilitec monitoring. Improvements were also observed for nighttime heartburn severity at Week 4. A greater percentage of IW-3718-treated patients (9 patients, 19.6%) reported an absence of heartburn during Week 4 compared with those receiving placebo (5 patients, 10.6%).

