3.3.2 Removal of Patients from Therapy or Assessment

A premature discontinuation will occur when a patient who has signed the ICF ceases participation in the study, regardless of circumstances, before completion of the Treatment Period.

A patient will be considered to have completed the study after receiving 8 weeks of treatment and completing the End-of-treatment (EOT) Visit at Day 57. A window of +3 days will be allowed for the EOT visit; if a patient completes the EOT Visit prior to Day 57, this will be considered a protocol deviation.

Patients will be informed that they are free to withdraw from the study at any time and for any reason. The Investigator may remove a patient from the study if, in the Investigator's opinion, it is not in the best interest of the patient to continue the study. Patients may also be discontinued from the study by the Investigator or the Sponsor at any time for any reason, including the following:

- Failure to meet an inclusion/exclusion criterion that is clinically relevant and affects patient safety
- Adverse event(s)

- Protocol violation, including lack of compliance
- Insufficient therapeutic response (lack of efficacy)
- Lost to follow-up (every effort must be made to contact the patient; a certified letter must be sent)
- Withdrawal of consent (attempts should be made to determine the reason for the patient withdrawing consent if possible)
- Study termination by the Sponsor
- Other reasons (e.g., administrative reasons or pregnancy)

The date the patient is withdrawn from the study and the reason for discontinuation will be recorded on the study termination form of the electronic case report form (eCRF). Patients who discontinue from the study for any reason should complete the assessments required at the EOT Visit at the time of their discontinuation. Patients who discontinue from the study will be followed until resolution of all of their AEs or until the unresolved AEs are judged by the Investigator to have stabilized. Study centers should make a reasonable effort to follow any pregnant patients until delivery or end of the pregnancy.

If a patient does not return for a scheduled visit, the study center should contact the patient. An effort must be made to contact the patient, including sending a certified letter. In every case, the patient outcome, including lost to follow-up information, will be documented.

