3.7.5.1 Adverse Events

Adverse event verbatim terms will be coded using the most current version of Medical Dictionary for Regulatory Activities (MedDRA) available at the start of the study. An AE (classified by preferred term) will be considered a TEAE if the AE onset date was after initial study medication administration and within 1 day of the last dose of study medication. The

number and percentage of patients reporting TEAEs will be tabulated by system organ class (SOC), preferred term, and treatment group. The number and percentage of patients reporting TEAEs will also be tabulated by SOC, preferred term, severity, and treatment group. Listings will be provided for deaths (if any), severe AEs, drug-related AEs, SAEs, and AEs leading to study discontinuation.

If a patient has more than 1 TEAE coded to the same preferred term, the patient will be counted only once for that preferred term. For the analysis of TEAEs by severity, the patient's highest severity TEAE within a preferred term will be used.

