1. INTRODUCTION

This statistical analysis plan (SAP) provides a more technical and detailed elaboration of the statistical analyses of the efficacy and safety data as outlined and/or specified in the amended protocol of Study [ICP-3718-202](#) (dated 27 July 2016). Specifications for the tables, figures, and data listings are contained in a separate document.

[figure not shown]

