4.3 SAFETY ASSESSMENTS

4.3.1 Adverse Events

An adverse event (AE) is any untoward medical occurrence in a patient. All AEs will be captured from the time the patient signs the informed consent until 7 days following the EOT Visit.

For all AEs, the investigator will provide an assessment of causal relationship to study medication (related or unrelated) and an assessment of the severity (mild, moderate, or severe). All AEs will also be categorized as serious or non-serious.

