5.13 DETERMINATION OF SAMPLE SIZE

The sample size per arm was determined by estimating the overall power of a linear trend test in a one-way design that included placebo and all the active treatment arms (500 mg BID, 1000 mg BID, and 1500 mg BID of IW-3718). The efficacy endpoint of interest in the previous Phase 2a study (ICP-3718-201) was change from baseline in daytime heartburn defined as the presence of heartburn since the patient awoke that morning (assessed in the evening) and assessed with an 11-point [0 to 10] NRS, where 0=none and 10=very severe. In that study, IW-3718 demonstrated treatment differences near 0.70 points for change over the treatment period (e.g., -0.73 vs. -1.38 for placebo and IW-3718, respectively), and standard deviations near 1.35 for the LSMS.

Employing these historical values, a study with 58 patients per arm (the expected number of patients at Week 8 given an enrollment of 260 patients) will have statistical power of at least 80% for the overall trend test (i.e., linear contrast) where the highest active treatment arm reflects 110% of the previously observed treatment difference and the lowest 2 active treatment arms reflect 55% of the same (two-sided, $\alpha=0.05$). At the proposed sample size, a subsequent pairwise comparison between placebo and an active treatment arm reflecting the previously observed treatment difference will have 80% statistical power (two-sided, $\alpha=0.05$).

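### The only onset statistic the SAP names for constipation, a Kaplan-Meier median, would almost certainly be 'not reached' at 1000 mg BID and on placebo at the Phase 2a rate; landmark cumulative incidence would be a cheap improvement

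*SAP*

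**What the plan says.** SAP 5.12.1 treats constipation as an adverse event of interest. On timing it has one sentence: "Median time from study drug initiation to onset of the first occurrence of constipation will be estimated using the Kaplan-Meier method". It names no curve, landmark or other quantile, no censoring rule, and no fallback if the median does not exist. The same section plans the incidence of treatment-emergent events by preferred term and a summary of constipation duration. SAP 5.10.3 summarizes the GSRS constipation domain by visit. SAP 1 adds that "Specifications for the tables, figures, and data listings are contained in a separate document".

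The only constipation rate is in Protocol 1.2, for a 4-week study of 1000 mg BID against placebo: "included constipation (13% vs 0" (per cent, IW-3718 first). The group sizes follow from "Safety and efficacy data are available for 93 patients, 46 of whom received 1000 mg IW-3718 BID".

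The documents do not agree on when onset stops counting. Protocol 3.7.5.1 requires onset "after initial study medication administration and within 1 day of the last dose of study medication". SAP 5.12.1 sets no end, and also counts an event that began before dosing and then worsened. SAP 4.3.1 says "All AEs will be captured from the time the patient signs the informed consent until 7 days following the EOT Visit". SAP 6, which lists changes from the protocol, does not mention the difference.

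**The concern.** A median onset time is informative only when about half the patients have the event. If far fewer do, the result is 'not reached', which says that fewer than half were affected but not whether constipation starts in the first days or builds up over 8 weeks. The other planned outputs do not fill that gap: incidence says how many, duration says how long, and the GSRS domain is a symptom score at Randomization, Week 4 and EOT. The stakes are modest: one descriptive summary of the one event the SAP marks out for extra attention.

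**Working it through.** Notation: t is days after first dose, so Day 57 is t = 56.

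**1. Reproduce the Phase 2a figure.** Placebo group: 93 − 46 = 47. 6/46 = 13.0%, while 5/46 = 10.9% and 7/46 = 15.2%, so the counts are 6/46 and 0/47. The same denominators return the other rates in Protocol 1.2: 9/46 = 19.6% and 5/47 = 10.6%.

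**2. What the median needs.** The Kaplan-Meier estimate must fall to 0.5. In an arm of 65 without censoring that is 33 events (32/65 = 49.2%, 33/65 = 50.8%).

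**3. Project to this trial (constant hazard assumed).**
- h = −ln(1 − 6/46)/28 = 0.00499 per day.
- F(t) = 1 − exp(−ht): 13.0% at t = 28, 24.4% at t = 56, 27.0% at t = 63, 28.1% at t = 66.
- Expected events by Day 57: 65 × 0.244 = 15.9. Expected median: ln 2/h = 139 days, or 19.8 weeks.
- To bring the expected median to the end of follow-up, the hazard would have to be ln 2/(56h) = 2.5 times as high for Day 57, or ln 2/(66h) = 2.1 times for t = 66.

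**4. Chance that the median is reached.** Exact 95% limits for 6/46 are 4.9% to 26.3%. The upper limit gives 1 − (1 − 0.2626)² = 45.6% at 8 weeks. The simulation uses n = 65, exponential onset, and exponential dropout of 7/65 by t = 56, from "58 patients per arm (the expected number of patients at Week 8 given an enrollment of 260 patients". In the spread rows the end of follow-up is uniform over whole days, because "A window of +3 days will be allowed for the EOT visit".

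| End of follow-up | At 6/46 | At upper limit |
|---|---|---|
| Day 57 for all (t = 56) | about 0.001% or less | 0.24–0.25 |
| Protocol window: EOT + 1 day (t = 57–60) | 0.03% | 0.37 |
| EOT + 7 days, no spread (t = 63) | 0.006% | 0.47 |
| EOT + 7 days, with spread (t = 63–66) | 0.07% | 0.57 |

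Other ways of handling whole-day onset times and the EOT spread raise the middle column to at most about 0.3%; the right-hand column stays at roughly 0.25 to 0.6. The plain binomial check P(X ≥ 33 of 65) at t = 56 gives 4 × 10⁻⁶ and 0.24. If no new cases arose after Week 4 (13.0%, 8.5 events), it is 3 × 10⁻¹³, so the result does not rest on the extrapolation.

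**5. Placebo.** The upper 95% limit for 0/47 is 7.5% in 4 weeks, hence 14.5% at 8 weeks. P(X ≥ 33 of 65) = 6 × 10⁻¹² at t = 56 and 4 × 10⁻¹⁰ at t = 66.

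**6. What landmarks would give at 6/46** (rounded expected counts, censoring ignored, exact 95% CI; the pooled column assumes that all three doses share this rate, for illustration only).

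| Landmark | One arm of 65 | IW-3718 overall, 195 |
|---|---|---|
| Day 15 | 4 events: 1.7–15.0% | 13 events: 3.6–11.1% |
| Day 29 | 8 events: 5.5–22.8% | 25 events: 8.5–18.3% |
| Day 57 | 16 events: 14.8–36.9% | 48 events: 18.7–31.3% |

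The share of Day 57 events that had started by Day 15 would have a 95% CI of 15–42% overall (13/48) and 7–52% in one arm (4/16). With no events in 65 the exact upper limit is 5.5%.

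**The case against.** - **'Not reached' is a legitimate Kaplan-Meier result, and a curve may already be planned.** Both parts stand. The method is sound, and the separate specifications, which are not among the documents, may contain a curve that shows the timing. The SAP text still names only the median.
- **The rate rests on six events.** This stands as a limit on the claim. Averaging over the uncertainty in the rate (Beta(6.5, 40.5), an assumption) raises the chance of reaching the median to about 1.4% to 4.4%, and at the upper 95% limit it is roughly 25% to 60%. 'Well under 1%' is conditional on the point estimate.
- **A reader might infer that the median fails in every arm.** The documents do not support that. They give no rate for 500 or 1500 mg BID.
- **A reader might infer that landmarks up to Day 57 avoid the question of the onset window.** They do so only for patients treated to Day 57. Someone who stops on Day 20 and becomes constipated on Day 25 falls outside the Protocol window, but may count at Day 29 under the SAP, which sets no end. With 7 of 65 expected to leave each arm, the window matters. So does the SAP's inclusion of worsening events.
- **Landmarks will not show onset by dose.** This largely stands: an early share of 7–52% in one arm hardly separates patterns.
- **The stakes are small.** Agreed. Safety analysis is descriptive under Protocol 3.7.5, and incidence and duration are already planned.

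**Conclusion.** The point holds as a minor one. At the Phase 2a rate, with a constant hazard and 65 patients per arm, the median has well under a 1% chance of being reached at 1000 mg BID and a negligible chance on placebo. The SAP text would then supply no timing of onset for those two arms. If the true rate is near the upper 95% limit, whether a median is reported turns partly on an end of follow-up that SAP 5.12.1 does not state. A reader might go further and infer that constipation goes unanalysed or that the safety conclusions are at risk. The documents do not support that: incidence, duration and the GSRS domain remain, and no test or decision rule uses this median.

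**What to change.** Replace the sentence in SAP 5.12.1 with:

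> Time to first treatment-emergent constipation (TEAE as defined in this section) will be summarized descriptively by Kaplan-Meier cumulative incidence at Days 15, 29 and 57, with 95% CIs (exact binomial limits in a group with no event), for each treatment group and for IW-3718 overall. Patients without an event are censored at the end of the TEAE onset window. The median will be given only if reached.

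State one TEAE onset window in the same section. It should reconcile Protocol 3.7.5.1 (1 day after last dose) with the SAP (no stated end, collection to 7 days after EOT), and the SAP should not claim that the landmarks are independent of that choice. Record any departure from the Protocol definition in SAP 6.

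Cost: a short SAP edit and a slightly larger table from the same data, with no added test. Per-arm estimates will be imprecise (about 4 of 65 events by Day 15 at the Phase 2a rate), so the landmarks describe onset mainly for IW-3718 overall. If the table and figure specifications already show the curve, only the SAP sentence needs to match them. Priority: optional improvement.

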3.6.3 Follow-up

The study site will contact all patients via telephone 7 days following the EOT Visit in order to collect information regarding ongoing AEs and/or SAEs and any new AEs and/or SAEs since the EOT Visit (Section 3.5.1.3).

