5.1.2 Handling of Missing Values

Unless stated otherwise, missing data will not be imputed.

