7.5 MISSING DATE INFORMATION FOR ADVERSE EVENTS

The following imputation rules apply to cases in which the start date is incomplete (i.e., partial missing) for adverse events.

a. If AEs occurred during the Screening or Pretreatment Period (i.e., the Screening or Pretreatment Period is checked on the AE eCRF)

Missing day and month

- If the year is the same as the year of the date of informed consent, then the day and month of the date of informed consent will be assigned to the missing fields.
- If the year is prior to the year of the date of informed consent, then December 31 will be assigned to the missing fields.
- If the year is after the year of the date of informed consent, then January 1 will be assigned to the missing fields.

Missing month only

- The day will be treated as missing and both month and day will be replaced according to the above procedure.

Missing day only

- If the month and year are the same as the month and year of the date of informed consent, then the date of informed consent will be assigned to the missing day.
- If either the year is before the year of the date of informed consent or if both years are the same but the month is before the month of the date of informed consent, then the last day of the month will be assigned to the missing day.
- If either the year is after the year of the date of informed consent or if both years are the same but the month is after the month of the date of informed consent, then the first day of the month will be assigned to the missing day.

If the stop date is complete and it is before the date of randomization and the imputed start date as above is after the stop date, the start date will be imputed by the stop date. If the stop date is complete and it is on or after the date of randomization and the imputed start date as above is after the stop date, the start date will be imputed by the date immediately before the date of randomization.

If the start date is completely missing, then the date of informed consent will be used to impute the start date.

b. If AEs occurred during the Treatment Period (i.e., the Treatment Period is checked on the AE eCRF)

Missing day and month

- If the year is the same as the year of the date of the first dose of double-blind study drug, then the day and month of the date of the first dose of double-blind study drug will be assigned to the missing fields.

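### The SAP gives no way to handle constipation still ongoing at last contact, so the planned duration summary risks being too short

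*SAP*

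**What the plan says.** SAP 5.12.1 plans two constipation analyses. For onset: "Median time from study drug initiation to onset of the first occurrence of constipation will be estimated using the Kaplan-Meier method". For duration: "Duration of treatment-emergent constipation will also be summarized", and where a patient has several occurrences, "the occurrence with the longest duration will be used in the summary". The duration sentence names no estimator, no end-date definition and no rule for an ongoing event. SAP 5.1.1 then supplies the default for a continuous variable: number, mean, SD, median, minimum and maximum.

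Three other SAP sections bear on an event with no stop date:

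- 5.1.2: "Unless stated otherwise, missing data will not be imputed".
- 7.5: "The following imputation rules apply to cases in which the start date is incomplete (i.e., partial missing) for adverse events". It has no counterpart for AE stop dates. Section 7.6.2 does have stop-date rules, but for medications only.
- 4.3.1: "All AEs will be captured from the time the patient signs the informed consent until 7 days following the EOT Visit". Footnote n of the SAP schedule (Table 4.4-1), and the same footnote in the protocol schedule, ends AE capture at the EOT Visit instead.

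On follow-up, protocol 3.6.3 says "The study site will contact all patients via telephone 7 days following the EOT Visit". Protocol 3.3.2 says "Patients who discontinue from the study will be followed until resolution of all of their AEs", or until the investigator judges unresolved events to have stabilised.

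**The concern.** Time from onset to resolution is right-censored when collection stops before the event does. The SAP recognises censoring for time to onset but provides nothing for duration. An ongoing episode has a known start and no end, so its length cannot be computed under the written rules. If it is omitted, the events lost are disproportionately the long ones. If the patient also had a resolved episode, that shorter one can be taken as the longest. If the ongoing episode is cut off at last contact and treated as complete, its length is understated. All three push the summary the same way.

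At stake is the description of how long constipation lasts at each dose, in a trial whose objectives include safety and dose response. The shortening is greatest in the arm with the most persistent or latest-starting constipation, so a difference between doses in persistence would look smaller than it is. No efficacy conclusion is affected.

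**Working it through.** The documents state no duration figure, so there is none to reproduce. The check has three parts.

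**1. Last contact.** EOT is Day 57, with a window of +3 days (protocol 3.3.2). The call 7 days later falls on Day 57 + 7 = 64 to Day 60 + 7 = 67. If schedule footnote n governed, collection would end at Day 57 to 60. Day 64 is used below.

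**2. Size, under assumptions that are not in the documents.** Onset is uniform over 56 days. Duration is exponential with median M, so λ = ln 2 / M. The resolution rate does not change after the last dose. Time from onset to last contact, C, is then uniform on 8 to 64 days.

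- Share ongoing = (e^(−8λ) − e^(−64λ)) / (56λ).
- Resolved-only median m (for m > 8) solves 1 − [(e^(−8λ) − e^(−mλ))/λ + (64 − m)e^(−mλ)]/56 = ½ × (1 − share ongoing).
- Median t when ongoing events are cut off at C and treated as complete (for t > 8) solves e^(−λt)(64 − t)/56 = ½.

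For M = 14: λ = 0.0495, e^(−8λ) = 0.673 and e^(−64λ) = 0.042. Share ongoing = (0.673 − 0.042)/2.773 = 0.23. With m = 9.9 the left side is 0.386, which is half of the resolved share of 0.772. The cut-off median is 12.4.

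| True median (days) | Ongoing at Day 64 | Resolved-only median | Cut-off median |
|---|---|---|---|
| 7 | 8% | 6.2 | 7.0 |
| 14 | 23% | 9.9 | 12.4 |
| 28 | 44% | 13.4 | 19.1 |
| 56 | 65% | 16.0 | 25.6 |

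In a parallel simulation with true medians of 4.9, 9.7, 19.3 and 38.8 days, Kaplan-Meier with censoring at last contact returned 4.9, 9.7, 19.3 and 38.9.

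**3. Sensitivity to the assumptions.**

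- *Early onset* (mean about Day 10): a true median of 7 is reported as 6.9, and 14 as about 12.5.
- *Resolution after the last dose* (uniform onset; events open at Day 56 then resolve with an assumed median of 3 days): for on-drug medians of 14, 28 and 56 days, 5%, 9% and 11% are ongoing. The resolved-only medians are 10.7, 16.2 and 21.6, against true medians of 11.4, 17.5 and 23.2. With an off-drug median of 5 days, the 56-day case gives 24% ongoing and 21.2 against 25.3.

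**Case numbers.** Protocol 1.2 reports constipation in 13% of Phase 2a patients on 1000 mg BID. At that rate 0.13 × 65 = 8.45, or about 8 cases per active arm, and 0.13 × 195 = 25.35, or about 25 over three arms. A few ongoing cases can therefore move an arm's median.

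**The case against.** The strongest reply is that nothing biased has been planned. The SAP nowhere restricts the summary to events with a stop date. A reader might infer that rule from 5.1.2 and 7.5, but a known ongoing event is censored rather than missing, 7.5 concerns incomplete start dates, and cutting off at last contact is equally compatible with the text. SAP section 1 also places table and listing specifications in a separate document, where a convention could sit. This stands: the defect is a missing method, not a stated exclusion. It does not remove the point, because both obvious ways of filling the gap shorten duration.

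The second reply is that the larger figures in the table need constipation to ignore withdrawal of the drug. The last dose is taken on the morning of EOT, so the call follows a week off treatment. Part 3 of the working shows the shortfall shrinking sharply if episodes resolve off drug or start early. This also stands.

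Third, a reader might infer that the order of the doses could be reversed. In every row of the table the order is kept. A reversal would need arms that also differ in onset pattern, and the documents give no basis for that.

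Fourth, unequal follow-up might suggest that long events are measured in patients who stop and lost in those who complete. That overstates it. Follow-up after discontinuation may end at stabilisation, which also leaves no stop date, and censoring at each patient's own last contact accommodates unequal follow-up.

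Finally, this is an untested descriptive summary in a trial the protocol calls exploratory, and constipation incidence is tabulated separately. That limits the weight of the point.

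**Conclusion.** The concern holds as a gap in method. SAP 5.12.1 plans a plain summary of a duration that can be censored, and the SAP's defaults leave an ongoing episode without a length. Omission, substitution of a shorter episode and cut-off at last contact all bias the result short.

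The size cannot be fixed from the documents, because neither the share ongoing nor the durations are given. It runs from negligible (short or early episodes) to large (long episodes that persist after dosing ends). The 14-day row, 9.9 reported against 14, is an illustration conditional on its three assumptions, not a forecast. The longest-occurrence rule defines which quantity is described; it does not compensate for losing the ongoing episodes. This is a low-cost improvement to a safety description, not a threat to the trial's main conclusions.

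**What to change.** In SAP 5.12.1:

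1. Keep the longest episode as the quantity described, and estimate its duration by Kaplan-Meier. Treat an ongoing episode as lasting at least its observed length and censor it at the patient's last AE contact.
2. Report, by arm, the number and percent of patients with constipation ongoing at last contact.
3. Reconcile the end of AE collection: 7 days after EOT in SAP 4.3.1, the EOT Visit in schedule footnote n. The censoring date depends on it.

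The longest-episode target should stay, since moving to the first episode would describe something else. A common 7-day cut-off for discontinued patients is not needed either: it would discard follow-up the protocol collects.

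The cost is a few sentences and one table; no new data are needed. The drawback is that, with about 8 cases per active arm, the Kaplan-Meier median may not be reached where constipation persists: in about half of simulated arms of 8 at a true median of 56 days. The ongoing percentage covers that situation.
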